### Withdrawal due to loss of capacity

Cognitive status would usually be monitored by a medical practitioner at a clinical visit using a clinical assessment tool such as the Mini-Mental State Examination (MMSE) or similar. Since this study is conducted remotely, cognitive ability of participants will be monitored through an existing algorithm which is built into the PROTECT system. It is based on completion of the cognitive tests described above which are considerably more sensitive to change than the MMSE. Any participant flagging as performed more than one standard deviation below age-matched norms on two cognitive tests in two consecutive assessments will be reviewed by one of two named study doctors ([name] / [name]). If concerns are considered to be valid the participant and their GP will be contacted by the study doctors to recommend further assessment, and the participant will be withdrawn from the trial.

### Withdrawal procedure

At the point of withdrawal participants will receive notification by email. Anonymised data will be retained. Participants will have the option to remove all personal data with the exception of the minimum required for record of consent. Participants will be sent a pre-paid envelope to return any unused tablets for disposal.

## 7.12 End of trial participation

End of trial is defined as the last assessment point completed by the last participant to enrol in the study or six weeks after the last participant's last time point if the last assessments are not completed.

## 8 TRIAL TREATMENTS

### 8.1 Name and description of investigational medicinal product(s)

Vitamin D capsule single dose (4000IU)

### 8.3 Product Characteristics

Composition: Microcrystalline cellulose [*bulking agent*], Vitamin D3 preparation (Maltodextrin, Starch, Sucrose, Cholecalciferol), Hydroxypropyl methyl cellulose [*Capsule*], Magnesium stearate [*anti caking agent*], Silicon dioxide [*anti caking agent*]

Preparation: Two-piece HPMC capsules, provided in blister packs of 28 capsules stamped with the day of the week to aid compliance

### 8.4 Supplement storage and supply

Vitamin D tablets and placebo will be manufactured by HealthSpan Ltd and packaged in blister packs of 28 pills, with days of the week marked on the packet. The shelf life of capsules is a conservative two years, but to ensure dosing capsules will be delivered quarterly unless the government COVID-19 alert is level 2 or higher in which case a larger supply will be sent to mitigate against the risk of site closure due to a lockdown. Capsules can be stored at room temperature with no additional special requirements.

### 8.5 Preparation and labelling of Supplement

Blister packs of study supplements will be labelled with the participant ID and batch number. The Clinical Trials Unit at the University of Exeter will provide recording and mail-out services. The CTU is fully registered and qualified as a research facility and is fully compliant in participant confidentiality procedures. Postage will comply with regulations pertaining to mailing of research/hazardous materials, using pre-labelled envelopes, sealed boxes and tracked delivery. The randomisation schedule will be directly accessed through REDCap Cloud by the Clinical Trials Unit staff member who will be unblinded to treatment allocation. This staff member will be responsible for labelling and sending out trial tablets, recording dispensing and reporting back to the VitaMIND team to ensure dispensing activity is recorded in the study database.

### 8.6 Dosage schedules

Participants will be instructed to take one tablet per day for two years. For the active supplement each dose will contain 4000IU of Vitamin D3.

### 8.7 Known drug reactions and interaction with other therapies

Possible severe interaction with Digoxin. Participants taking this medication will be excluded from the trial.

*Guidance on taking supplements:* Participants will be instructed to take one tablet per day. There are no known side effects of vitamin D supplementation within the dose used in this study. In the event of an extreme overdose (usually occurring after taking consistent high doses of 60,000IU per day for several months) symptoms include nausea and vomiting, weakness and frequent urination, followed by osteopain and kidney complications. This is extremely unlikely to occur within this trial but participants will be guided to be aware of symptoms in case of an overdose and provided with clear signposting to contact their GP for support if this occurs, in addition to reporting the event to the study administrator.

### 8.11 Assessment of compliance with treatment

**Compliance Monitoring:** Monitoring of participant use of the tablets will be achieved through a 'medication diary' on the PROTECT site which will ask participants to provide a quarterly tablet count, both of which will be entered online. This will also be supported through reminder emails and regular newsletters from the PROTECT study. This process is anticipated to be highly effective. However, since it is reliant on participant adherence and fidelity, an additional sub-group of compliance testing will also be performed (see below).

**Sub-group Compliance Monitoring:** In addition a sub-group of 10% of the total cohort (n = 58) will be recruited to complete a finger prick test to analyse blood levels of Vitamin D3 metabolites at baseline and primary endpoint (24 months) as a further compliance measure. This process will be delivered through partnership with the Sandwell and West Birmingham NHS foundation Trust test facility. This process will involve:

- Sub-group compliance participants allocated to the first 10% of randomised participants
- Study administrator attaches participant identifier label to test kit and posts kit to participant
- Participants will receive a test kit to complete at home, involving a short finger prick test
- Participants use pre-addressed envelope to send their completed test to the Sandwell and West Birmingham NHS Foundation Trust test laboratory
- Laboratory completes Vitamin D3 analysis according to published protocols using anonymised sample identifiers. No sample is retained after analysis
- Laboratory returns anonymised test results to study team

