## 7 TRIAL PROCEDURES

### 7.1 Recruitment

#### 7.1.1 Participant identification

Recruitment of participants will be achieved through the PROTECT study cohort. The study operates entirely online, with existing participants receiving email reminders to log in and complete outcome assessments or register for new trials. All participants have given consent for contact and have full datasets for pre-screening. The PROTECT study has existing ethical approval (Ref: 13/LO/1578) and has been running since April 2015.

Participants with dementia risk will be identified anonymously through pre-screening of the existing PROTECT database. This will involve identification of people fulfilling the criteria for AACD through screening of cognitive test scores, those fulfilling criteria for family history through self-reported data provided on family history of dementia and those with subjective concerns about their cognitive health. Participants in the PROTECT study will be contacted via email and invited to take part in VitaMIND. The email will contain a link to the dedicated trial section of the site. Individuals known to fulfil the AACD and family history criteria will be automatically flagged for eligibility by the online system. Participants will also be asked if they have subjective concerns about their cognitive health in order to capture this third eligibility criterion. In the event that additional recruitment is required new participants will be approached through NHS Trust memory clinics, the Exeter 10,000 cohort of older adults (existing approval and consent for contact), through partner platforms such as Join Dementia Research (an online self-registration service that enables volunteers with memory problems, carers of those with memory problems and healthy volunteers to register their interest in taking part in research), and through national publicity.

10% of the study cohort will be randomly selected for compliance testing via a finger prick blood test. Participants in this sub-group will confirm their willingness to participate in the blood testing during registration and those selected will be sent a blood test kit in their welcome pack.

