### 7.4 Blinding

Treatment allocation of participants will be recorded electronically in REDCap Cloud which is hosted by the University of Exeter's Clinical Trials Unit. This will ensure that both participants and research team will be blind to allocation, thus removing any bias. Administrative staff on the overall PROTECT study team that have direct participant contact will not be involved in any data analysis in order to avoid any unconscious bias as a result of their contact.

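### The 24-month vitamin D results of the compliance sub-group go to a study team that should be blind, with no hold-back, and could reveal allocation for up to 58 participants before database lock

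*Protocol*

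**What the plan says.** Section 8.11 adds a blood test to the tablet counts, to "analyse blood levels of Vitamin D3 metabolites at baseline and primary endpoint (24 months) as a further compliance measure". The sub-group is 10% of the cohort, 58 people. The study administrator labels each kit with the participant identifier, the participant posts the sample, and the laboratory works with anonymised sample identifiers. The last step is "Laboratory returns anonymised test results to study team". Neither a return date nor a hold-back is stated.

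Section 7.4 says of the electronic allocation record: "This will ensure that both participants and research team will be blind to allocation, thus removing any bias".

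Section 8.5 does set up a separation for dispensing. One Clinical Trials Unit (CTU) staff member is unblinded and handles labelling and dispatch. The blood results are not routed to that person.

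The protocol describes the selection of the sub-group in two ways. Section 7.1.1 says "10% of the study cohort will be randomly selected for compliance testing via a finger prick blood test", and section 8.11 says "Sub-group compliance participants allocated to the first 10% of randomised participants".

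**The concern.** The active arm takes 4000 IU of vitamin D3 daily for two years (section 8.6) and the other arm takes placebo. A vitamin D level after that period is therefore a marker of allocation as well as of compliance. Following section 8.11 as written gives this marker to people whom section 7.4 requires to be blind.

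The word anonymised does not prevent this. It protects privacy. To serve as a compliance measure, the baseline and 24-month values must be paired within a participant, and the kit label makes that link possible.

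Three judgements could still be open when the 24-month results arrive:

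- causality review of events reported late in follow-up (sections 9.3 and 9.4);
- data handling before database lock;
- the per-protocol definition for the complier average causal effect (CACE) analysis, which section 10.3 leaves to the Trial Management Group (TMG) to settle before analysis. This is the most direct exposure, because those defining compliance could already have seen a compliance measure that also hints at the arm.

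**Working it through.** **1. Size of the sub-group.** Inputs: 10% (section 8.11) and 584 participants (section 10.1). 0.10 × 584 = 58.4, so 58. The protocol's figure reproduces. With the 20% drop-out assumed in section 10.1, about 0.80 × 58 = 46 would still be in the trial at 24 months, so 58 is an upper limit.

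**2. Which sample is informative.** There are two samples. Baseline, if taken before the first capsule, has the same expected distribution in both arms and reveals nothing. The 24-month sample is the only one after treatment starts, and it falls when that participant's dosing and primary endpoint are due.

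**3. When the 24-month results could arrive.** Inputs: 300 recruits per month and a three-month window that may be extended (section 10.2), and 4.345 weeks per month. The gap between the 58th and the 584th participant reaching month 24 is:

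- at 300 per month: (584 − 58)/300 × 4.345 = 7.6 weeks;
- spread evenly over three months: 3 × 4.345 × (584 − 58)/584 = 11.7 weeks.

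This is about 8 to 12 weeks, and longer if recruitment is extended. Posting, home sampling and laboratory turnaround shorten it. If the sub-group is instead a random 10%, as in section 7.1.1, the average gap is half the recruitment period: (584/300 × 4.345)/2 = 4.2 weeks, or (3 × 4.345)/2 = 6.5 weeks. On either reading, most results could precede the last participant's final assessment. Database lock comes later still.

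**4. How much one result reveals.** The protocol gives no expected level, SD or difference, so the separation d, in SD units, is an assumption. With 1:1 allocation, normal distributions of equal SD and a cut at the midpoint, the probability of naming the arm correctly is Φ(d/2).

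| Assumed d | Φ(d/2) | Expected correct out of 58 |
|---|---|---|
| 0 (baseline, or blind) | 0.50 | 29 |
| 0.5 | 0.60 | 35 |
| 1 | 0.69 | 40 |
| 2 | 0.84 | 49 |
| 3 | 0.93 | 54 |

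**5. The sections side by side.** Section 7.4 requires blindness. Section 8.5 keeps allocation knowledge with one CTU staff member. Section 8.11 sends a marker of allocation around that person to the study team. The conflict lies in the stated routing rule, so it is more than a detail left for another document.

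**The case against.** The strongest reply is that little bias can follow. Outcomes are self-completed online and no study-team rater is described. Section 10.3 states that the statistician is blinded, and section 7.4 keeps administrative staff with participant contact out of the analysis. At most 58 of 584 participants are affected, and only once their own 24 months are over. Most of their events will have been reviewed on receipt, before an informative result exists. The TMG may also have fixed the per-protocol definition by then. All of this stands, and it limits the point to the three exposures listed above. It does not remove the conflict between sections 7.4 and 8.11.

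Another reply is that withholding results from the TMG could hamper its safety review. An exception for an individual safety need, through section 7.5, meets this.

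A reader might infer more than the protocol supports:

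- **That participants are unblinded while on treatment.** No sample is taken between baseline and 24 months, and section 8.11 gives no return date. One can say only that results could arrive before the trial ends.
- **That a few inferred allocations would reveal others through batch numbers.** Section 8.5 says "Blister packs of study supplements will be labelled with the participant ID and batch number", but nothing states that batches differ by arm or that blinded staff see the numbers.
- **That loss-of-capacity withdrawals would be affected.** Under section 7.8 these begin with an algorithm applied to two consecutive assessments. For the tested participants month 24 is the last assessment, so there is almost nothing left to withdraw from, and their results do not reveal anyone else's arm.

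**Conclusion.** The point holds in a limited form. Section 8.11 returns a marker of allocation to a team that section 7.4 describes as blind, and states no hold-back. For up to 58 participants (10%), the 24-month result could indicate the arm before database lock. The probability of a correct guess is 69% to 93% if the arms differ by 1 to 3 SD, a range that is assumed and not taken from the protocol.

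The timing of about 8 to 12 weeks before the last participant finishes rests on the planned recruitment rate, on prompt return of results, and on the sub-group being the first 10% randomised.

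The likely bias in the primary outcome is small. The sample size and the primary analysis are unaffected. The change is still worth making, because the exposure comes from a stated rule and costs very little to close.

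**What to change.** Replace the last step of section 8.11 with wording such as: *Results go to the unblinded Clinical Trials Unit staff member (section 8.5) or are held at the laboratory. The 24-month results are withheld from the study team, the TMG and the blinded statistician until the per-protocol definition is final and the database is locked, except for an individual safety need handled through section 7.5.*

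Reconcile sections 7.1.1 and 8.11, so that the protocol gives one account of whether the sub-group is a random 10% or the first 10% randomised.

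The cost is one or two sentences. The unblinded role already exists, and no sample, assessment or analysis changes. The downside is that compliance blood results are seen later.

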## 9 PHARMACOVIGILANCE

### 9.1 Definitions

Term	Definition
Adverse Event (AE)	Any untoward medical occurrence in a participant to whom a medicinal product has been administered, including occurrences which are not necessarily caused by or related to that product.
Adverse Reaction (AR)	
An untoward and unintended response in a participant to an investigational medicinal product which is related to any dose administered to that participant.
 
The phrase "response to an investigational medicinal product" means that a causal relationship between a trial medication and an AE is at least a reasonable possibility, i.e. the relationship cannot be ruled out.
 
All cases judged by either the reporting medically qualified professional or the Sponsor as having a reasonable suspected causal relationship to the trial medication qualify as adverse reactions. It is important to note that this is entirely separate to the known side effects listed in the SmPC. It is specifically a temporal relationship between taking the drug, the half-life, and the time of the event or any valid alternative etiology that would explain the event.

Serious Adverse Event (SAE)	
A serious adverse event is any untoward medical occurrence that:
 
 
• results in death
 
• is life-threatening
 
• requires inpatient hospitalisation or prolongation of existing hospitalisation
 
• results in persistent or significant disability/incapacity
 
• consists of a congenital anomaly or birth defect
 

	
Other 'important medical events' may also be considered serious if they jeopardise the participant or require an intervention to prevent one of the above consequences.
 
NOTE: The term "life-threatening" in the definition of "serious" refers to an event in which the participant was at risk of death at the time of the event; it does not refer to an event which hypothetically might have caused death if it were more severe.

Serious Adverse Reaction (SAR)	An adverse event that is both serious and, in the opinion of the reporting Investigator, believed with reasonable probability to be due to one of the trial treatments, based on the information provided.
Suspected Unexpected Serious Adverse Reaction (SUSAR)	
A serious adverse reaction, the nature and severity of which is not consistent with the information about the medicinal product in question set out in the reference safety information:
 
 
• in the case of a product with a marketing authorisation, this could be in the summary of product characteristics (SmPC) for that product, so long as it is being used within its licence. If it is being used off label an assessment of the SmPCs suitability will need to be undertaken.
 
• in the case of any other investigational medicinal product, in the investigator's brochure (IB) relating to the trial in question
 

NB: to avoid confusion or misunderstanding of the difference between the terms "serious" and "severe", the following note of clarification is provided: "Severe" is often used to describe intensity of a specific event, which may be of relatively minor medical significance. "Seriousness" is the regulatory definition supplied above.

## 9.2 Operational definitions for (S)AEs

### *Adverse Event*

An AE is defined as any medical event occurring to a participant during the two-year study that requires medical intervention.

### *Serious Adverse Event*

An SAE must fulfil the following criteria:

- Hospitalisation, excluding admission for scheduled and elective surgery
- Death
- Life-threatening condition, excluding conditions already in an unstable state at registration

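### Sections 9.1 and 9.2 define adverse and serious adverse events differently, and the protocol does not say which definition governs the 24-hour review and reporting

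*Protocol*

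**What the plan says.** Section 9.1 (Definitions) describes an AE as "Any untoward medical occurrence in a participant to whom a medicinal product has been administered", whether or not the product caused it. Its serious adverse event (SAE) entry has five listed criteria: death, threat to life, inpatient admission or a lengthened stay, an event that "results in persistent or significant disability/incapacity", and one that "consists of a congenital anomaly or birth defect". It adds that other important medical events "may also be considered serious if they jeopardise the participant or require an intervention to prevent one of the above consequences". A note at the end of 9.1 says that seriousness means the regulatory definition given there.

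Section 9.2 (Operational definitions) states both terms again. For AEs: "An AE is defined as any medical event occurring to a participant during the two-year study that requires medical intervention". For SAEs: "An SAE must fulfil the following criteria", followed by hospitalisation (not for scheduled and elective surgery), death, and a life-threatening condition (not if already unstable at registration).

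Section 9.3 gives SAEs a review by a study clinician within 24 hours. AEs are reviewed by at least two members of the Trial Management Group (TMG). Section 9.4 requires SAEs to reach the sponsor within 24 hours of awareness and leaves seriousness to medical judgement.

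**The concern.** A protocol may restate a general definition in operational terms, but the restatement should either agree with the general one or say that it replaces it. Here the two disagree on both AEs and SAEs, and 9.1 claims authority over seriousness just before 9.2 departs from it.

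The label decides what happens next. The 24-hour clinician review and the 24-hour sponsor report are written for SAEs only, so the same event could be expedited or not depending on which section the assessor follows. Monitoring safety is a stated tertiary objective, measured by AE and SAE reports (section 3.7). The TMG reviews those events, looks for patterns across them (section 9.4) and may end the trial early (section iv). Pattern review needs events classified by one rule.

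**Working it through.** No arithmetic applies beyond counting criteria. The two sections compare as follows.

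| Item | Section 9.1 | Section 9.2 |
|---|---|---|
| AE entry condition | Any untoward medical occurrence | Medical event needing a medical intervention |
| Death | Serious | Serious |
| Threat to life | Serious | Serious, unless the condition was unstable at registration |
| Hospitalisation | Admission or lengthened stay | Admission other than for planned surgery; lengthened stay not mentioned |
| Disability or incapacity | Serious | Absent |
| Congenital anomaly | Serious | Absent |
| Important medical events | May be judged serious | Absent |
| How the list is read | Events meeting a listed outcome | Must meet the criteria, with no *any of* wording |

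Of the five listed criteria in 9.1, one is unchanged, two are altered and two are missing (1 + 2 + 2 = 5). The optional sixth clause is also missing.

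Following particular events through sections 9.3 and 9.4:

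1. **Lasting disability, treated without admission, no threat to life.** Serious under 9.1. Under 9.2 it is an AE only. It is logged and goes to two TMG members, but neither 24-hour step applies.
2. **The same event with no medical intervention.** Serious under 9.1. Under 9.2 it is not an AE at all.
3. **Important medical event, treated without admission.** May be judged serious under 9.1. Under 9.2 that discretion is gone, and the event is an AE.
4. **Complication that lengthens a planned surgical stay without threatening life.** Serious under 9.1. Under 9.2 the admission is excluded and a lengthened stay is not named, so the event is not clearly an SAE.
5. **Congenital anomaly.** The lists differ here too, but entry is limited to people aged 50 and over (section 6.1), so this carries little practical weight.
6. **Symptom that needs no medical intervention.** An AE under 9.1, not under 9.2.

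Section 9.3 asks for the seriousness criteria to be recorded for each event, and section 9.4 asks for a judgement of seriousness. Neither names the list to be used. Read literally, the lead-in to the 9.2 list could even require all three conditions at once. That is surely not intended, but the wording allows it.

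**The case against.** The best defence is that the narrowing is deliberate. Section 2.1 says the product is not a medicinal product and the trial is not a CTIMP, while 9.1 is written in the language of medicinal products. A section headed as operational could be tailoring for a remote, self-reported trial. That is plausible, but the protocol does not say so. It keeps the full 9.1 list and says that list defines seriousness, so the conflict stands even if the narrowing was meant.

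Two further objections stand in part. Staff may in fact apply 9.1, since 9.4 relies on medical judgement; it therefore cannot be said that events will certainly be missed, only that the governing list is not named. A treated event that falls short of 9.2 seriousness is also not lost: section 9.3 has it logged, reviewed by TMG members and followed to outcome, and the sponsor is informed. What is at risk is the 24-hour handling.

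A reader might infer that 9.2 leaves out the very events most likely to differ between arms, because section 8.7 says of vitamin D excess that "symptoms include nausea and vomiting, weakness and frequent urination". The documents do not support this. Section 8.7 ties those symptoms to extreme overdose, usually 60,000 IU per day for several months, against the trial's 4,000 IU (60,000 / 4,000 = 15 times). It calls this extremely unlikely and states that there are no known side effects at the trial dose. It also sends participants with such symptoms to their GP and asks them to tell the study administrator, so there is a reporting route, although 8.7 does not class the symptoms as AEs. The kidney complications it names next would probably need intervention and so count under 9.2.

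**Conclusion.** The protocol contains two conflicting definitions of AE and of SAE, with no rule of precedence. Under 9.2, a disabling event without admission, death or threat to life falls outside both 24-hour steps, although 9.1 makes it serious. An important medical event loses the possibility of being judged serious. If such events need a medical intervention, they remain visible to the TMG as AEs.

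The size cannot be put as a number of events, because the protocol gives no event rates. The conclusion rests on the wording of sections 9.1 to 9.4 alone and assumes no separate procedure that names the governing list. It does not show that any event was missed, or that a comparison between arms is biased. The point should be corrected because the 24-hour safety steps depend on the label and the repair is small.

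**What to change.** Reconcile sections 9.1 and 9.2:

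- **SAEs.** Reword 9.2 so that meeting any one criterion suffices, and carry over the 9.1 seriousness list, including disability, lengthened hospital stay and the discretionary clause on important medical events. Keep the stated exclusion of scheduled and elective surgery. Say expressly whether the exclusion of conditions unstable at registration stays.
- **Precedence.** State that this list governs the 24-hour clinician review in 9.3 and the 24-hour sponsor report in 9.4.
- **AEs.** Settle on one definition and state that it governs what is recorded. If the wider one is chosen, record whether a medical intervention was needed as an attribute of each event, so that events collected before and after the change can be compared.

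The cost is protocol wording, somewhat more events to classify and expedite, and, if the wider AE definition is adopted, a possible change in ascertainment during follow-up. The last matters here: Appendix A says of version 8.0 that power for the two-year outcome had already been achieved, so the change would come late. That makes the AE part a genuine trade-off. The SAE part is not affected in the same way and should go ahead regardless.
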